5.7 Interim Analyses

No formal interim analyses are planned for this study.

6 SUPPORTING DOCUMENTATION

6.1 Appendix 1 List of Abbreviations

Table 10 List of Abbreviations

Abbreviation	Term
AE	adverse event
AESI	adverse event of special interest
ALP	alkaline phosphatase
ALT	alkaline aminotransferase
AST	aspartate aminotransferase
ATC	Anatomic Therapeutic Chemical
AUC	area under the curve
AUC _{0-24hr}	area under the plasma concentration-time curve from time 0 to 24 hours post-SUBLOCADE dose
AUC _{last}	area under the plasma concentration-time curve from time 0 to the time of the last quantifiable concentration
AUC _{inf}	area under the plasma concentration-time curve from time 0 extrapolated to infinite time
BLQ	below the limit of quantitation
BMI	body mass index
CI	confidence interval
C _{max}	maximum observed concentration
COWS	Clinical Opiate Withdrawal Scale
CRF/eCRF	case report form/electronic case report form
CSR	clinical study report
ECG	electrocardiogram
EOS	end of study
EOT	end-of-treatment
ET	early termination

Abbreviation	Term
FAS	full analysis set
GGT	gamma-glutamyl transferase
Hep	hepatitis
HIV	human immunodeficiency virus
hr(s)	hour(s)
KM	Kaplan-Meier
LD	lactase dehydrogenase
LFT	liver function tests
MedDRA	Medical Dictionary for Regulatory Activities
MMP	medical monitoring plan
N/A	not applicable
NMP	N-methyl-2-pyrrolidone
OC-VAS	Opioid Craving Visual Analogue Scale
OD	opioid use disorder
PK	pharmacokinetic(s)
PT	preferred term
SAE	serious adverse event
SAP	statistical analysis plan
SC	subcutaneous
SD	standard deviation
SOC	System Organ Class
T _{max}	time of maximum observed plasma concentration
TEAE	treatment-emergent adverse event
TLF	tables, listings and figures
TLFB	timeline follow back
TM BUP	transmucosal buprenorphine
UDS	urine drug screen
ULN	upper limit of normal
USPI	United States Prescribing Information
VAS	visual analogue Scale
WHO	World Health Organization
WHODD	World Health Organization Drug Dictionary

6.2 Appendix 2: Changes to Protocol-Planned Analyses

The main analytical approach for the analysis of increase in COWS total score of ≥ 6 from the pre-SUBLOCADE value is the Kaplan-Meier method. This method was described as a potential sensitivity analysis in version 1.0 of the SAP but is now specified as the main analysis given the extent of missing COWS assessments in the data. The endpoint is described accordingly as the cumulative event rate.

The protocol indicated that clinical laboratory tests assessed both at pre-SUBLOCADE and EOT would be summarized (Protocol Section 14.5.4). However, per the protocol schedule of assessments, clinical laboratory tests other than LFTs are only assessed at the screening visit. Therefore, tests other than LFTs are only listed.

The AUC formula has been corrected and details of the AUC analysis are provided to clarify imputation of missing COWS assessments, times used for the calculation, and to add normalization of the AUC.

The shift analysis of the investigator's assessment of ECGs is removed and the data will only be listed.

The protocol definition of precipitated withdrawal following TM BUP is corrected.

The pregnancy test result data will be listed only, and not summarized as stated in the protocol.

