14.2 Sample Size

Approximately 15 adult subjects with moderate to severe OUD are planned to be dosed with SUBLOCADE. If a subject prematurely discontinues from the study, additional subjects may be enrolled to ensure that 15 subjects are dosed with SUBLOCADE and are evaluable for precipitated withdrawal (see Section 14.3.1).

With a sample size of 15, the probability to observe at least one case of precipitated withdrawal is 79.4%, assuming the true event rate is 10%, while the probability to observe at least one case of precipitated withdrawal is reduced to 53.7% if the true event rate is 5%. Table 4 provides the probabilities of observed events at different true event rates.

Table 4 Probabilities of Observed Events at Different True Event Rates

| True Event Rate | 0 event | At Least 1 Event | At Least 2 Events | At Least 3 Events |
|-----------------|---------|------------------|-------------------|-------------------|
| 1% | 0.860 | 0.140 | 0.010 | 0.0004 |
| 5% | 0.463 | 0.537 | 0.171 | 0.036 |
| 8% | 0.286 | 0.714 | 0.340 | 0.113 |
| 10% | 0.206 | 0.794 | 0.451 | 0.184 |
| 15% | 0.087 | 0.913 | 0.681 | 0.396 |
| 20% | 0.035 | 0.965 | 0.832 | 0.602 |

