14.3 Analysis Populations

14.3.1 Full Analysis Set (FAS)

The FAS population consists of all subjects who receive a SUBLOCADE injection and are evaluable for precipitated withdrawal; i.e., having data for at least 1 COWS assessment before SUBLOCADE injection and COWS assessments for 48 hours after SUBLOCADE injection. The FAS will serve as the primary population for the analysis of key endpoints in this study.

14.3.2 *Safety Analysis Set*

The safety population will be used for the safety analysis, and it consists all subjects who received at least 1 dose of SUBLOCADE. The safety population will serve as the primary population for the analysis of other safety assessments.

14.3.3 *TM Buprenorphine Analysis Set*

The TM Buprenorphine Analysis Set consists of all subjects who received at least 1 dose of TM buprenorphine. This analysis set will be used for analysis of the exploratory safety endpoint.

14.3.4 *PK Analysis Set*

The PK Analysis Set will be used for the Exploratory PK endpoint analysis and will consist of all subjects who receive the SUBLOCADE injection and are evaluable for PK, i.e., having an adequate number of PK samples collected to derive PK parameters. Subjects in the PK population with protocol deviations or events that impact the quality of the PK data will be assessed on a case-by-case basis.

14.4 **Analysis of Key and Exploratory Endpoints**

14.4.1 *Key Endpoints*

The number and percentage of subjects who experience precipitated withdrawal (defined as an increase in COWS by ≥ 6 from the pre-SUBLOCADE value) within approximately 1 hour after SUBLOCADE administration will be summarized. The frequency count, percentage and its 2-sided 95% exact confidence interval (CI) using binomial distribution (Clopper-Pearson method) will be constructed for precipitated withdrawal from the pre-SUBLOCADE value, using the FAS.

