The number and percentage of subjects with ≥ 6 -point increase in COWS within the first 6, 12, 24, or 48 hours post SUBLOCADE administration will be summarized using the FAS. As this is a cumulative endpoint, once a subject has a ≥ 6 -point increase in COWS, the subject will be counted for that timepoint and all subsequent timepoints. The denominator at each timepoint will be the number of subjects who have a pre-SUBLOCADE COWS assessment and either 1) have a ≥ 6 -point increase in COWS at or before the timepoint, or 2) have at least one post-SUBLOCADE COWS assessment within the timepoint interval. COWS assessments occurring at unscheduled visits will be included in the derivation.

The AUC will be calculated using the linear trapezoidal method, i.e.,

$$AUC = \frac{1}{2} \sum_{i=0}^n (T_{i+1} - T_i)(C_{i+1} - C_i)$$

where T_i is the i^{th} time value, C_i is the i^{th} COWS score, and n is the number of time values. Inherent to this formula, missing COWS scores are imputed in a linear manner.

The area under the curve (AUC) of COWS score from the time of administration of SUBLOCADE (i.e., time 0) through 6, 12, 24 and 48 hours after SUBLOCADE administration will be calculated using the FAS, and summarized using descriptive statistics for continuous endpoints (e.g., n, mean, median, SD, minimum and maximum).

The total score on the COWS and opioid craving visual analogue scale (OC-VAS) during the treatment period (i.e. at each assessment timepoint from administration of TM buprenorphine at Day 1 through EOT) will be summarized using descriptive statistics for continuous endpoints for the absolute value and change from the pre-TM Buprenorphine and pre-SUBLOCADE values. The analysis will use the FAS and observed data.

14.4.2 *Exploratory Endpoints*

The number and percentage of subjects who experience precipitated withdrawal from TM buprenorphine (defined as an increase in COWS by ≥ 6 from prior to the most recent dose of TM buprenorphine before SUBLOCADE administration) will be summarized using the TM Buprenorphine analysis set. The number, percentage and its 2-sided 95% exact CI using binomial distribution (Clopper-Pearson method) will be constructed using observed data.

Peak and overall plasma exposure to NMP following a single SC injection of 300 mg SUBLOCADE will be evaluated. The following PK parameters for NMP will be derived by non-compartmental analysis:

- C_{\max} : maximum observed plasma concentration

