14.7 Handling of Missing Data

As described in Section 14.4, for the analyses of change in COWS ≥ 6 , observed COWS data will be used with no imputation. However, the cumulative summaries by definition carry forward a previous occurrence of COWS ≥ 6 .

For the analyses of absolute scores and changes in COWS total score and OC-VAS score, observed COWS and OC-VAS data will be used with no imputation. The AUC derivation for the COWS scores imputes missing scores in a linear manner.

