1.3 Study Design

SUBLOCADE™ (extended-release buprenorphine) injection for subcutaneous (SC) use is currently indicated for the treatment of moderate to severe opioid use disorder (OUD) in patients who have initiated treatment with a transmucosal (TM) buprenorphine-containing product to suppress opioid withdrawal signs and symptoms for a minimum of 7 days (SUBLOCADE United States Prescribing Information [USPI]). This study is to evaluate the safety and tolerability of starting SUBLOCADE treatment following a shorter period of TM BUP treatment.

This is a Phase 4, non-randomized, uncontrolled, open-label, single group, single center study in approximately 15 adult subjects with moderate or severe OUD.

Subjects who provide written informed consent will enter a Screening Period to confirm study eligibility. On Day 1, eligible subjects will check-in to undergo pre-buprenorphine assessments and be evaluated to receive TM BUP. If a subject's COWS is not ≥ 8 , the subject may either be re-scheduled for check-in within the Screening Period or remain in the clinic (at the Investigator's discretion), and the COWS may be repeated until the subject achieves a score ≥ 8 . Only when the COWS is ≥ 8 and all pre-buprenorphine assessments have been completed may the subject receive TM BUP.

One hour after the TM BUP dose, the subject will complete pre-SUBLOCADE assessments including: COWS (first, to assess precipitated withdrawal) and OC-VAS, then Sedation VAS, AEs, vital signs and concomitant medications.

Any subject who displays any allergic/hypersensitivity reaction to buprenorphine will be discontinued from the study and will be followed up via telephone call 24 to 72 hours post dose.

Subjects experiencing precipitated withdrawal will be treated for withdrawal symptoms. If precipitated withdrawal occurs before SUBLOCADE administration, the TM induction may be restarted later on the same day at the discretion of the Investigator, based on the half-life of the opioid reported on the Timeline Follow Back. Alternatively, the Investigator may permit the subject to return to the facility on another day (within the Screening Period). Returning subjects will repeat all Day 1 scheduled assessments.

If the subject does not display any allergic/hypersensitivity reaction or clinical signs of sedation, and does not experience precipitated withdrawal, 300 mg SUBLOCADE may be administered to the subject.

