5.3.3 COWS Total Score Increase – Sensitivity Analyses

5.3.3.1 Stratification Variables

If sample size permits, the cumulative event rate analysis will be repeated for each of three stratification variables: number of TM BUP doses during induction phase (1 dose, ≥ 2 doses) and during SUBLOCADE treatment phase (0 dose, ≥ 1 dose), and by enrollment before or after re-training (see [Section 5.6](#)).

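### After missing COWS data were seen, SAP v2.0 replaced the protocol's count and percentage of ≥6-point COWS increases with Kaplan-Meier and kept neither that count nor its exact 1 h interval as a sensitivity analysis

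*SAP*

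**What the plan says.** **Protocol.** Section 14.4.1 gives the planned analysis at 1 h: "The frequency count, percentage and its 2-sided 95% exact confidence interval (CI) using binomial distribution (Clopper-Pearson method) will be constructed for precipitated withdrawal", in the FAS. For 6, 12, 24 and 48 h it plans cumulative counts and percentages with a stated denominator: "The denominator at each timepoint will be the number of subjects who have a pre-SUBLOCADE COWS assessment" and who either have already had the event or "have at least one post-SUBLOCADE COWS assessment within the timepoint interval". Section 14.7 adds, for this endpoint, that "observed COWS data will be used with no imputation".

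**SAP.** Section 5.3.2 estimates the cumulative event rate by Kaplan-Meier on five key timepoints (1, 6, 12, 24 and 48 h), with events and censoring assigned by Table 7. The version history (SAP 1.1) dates the change to v2.0, 19 December 2019, and describes the missing assessments as unexpected. SAP 6.2 says Kaplan-Meier had been a possible sensitivity analysis in v1.0 "but is now specified as the main analysis given the extent of missing COWS assessments in the data".

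SAP 5.3.3 lists two sensitivity analyses for this endpoint. In the first, "the cumulative event rate analysis will be repeated for each of three stratification variables". The second is external adjudication of precipitated withdrawal by clinical judgement, reported with a Clopper-Pearson interval. Neither is the protocol's count of subjects meeting the 6-point rule.

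**The concern.** SAP 1.3 states: "This is a Phase 4, non-randomized, uncontrolled, open-label, single group, single center study". With no control arm and no hypothesis test, the event rate and its uncertainty are the result. The method for estimating that rate was changed because of something seen in the accruing data. The usual protection is to report the originally planned estimate beside the new one, so that a reader can see whether the change matters. Here the planned estimate was dropped instead of being moved to a sensitivity analysis.

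The two methods also treat missed assessments differently, so they need not agree. In addition, the protocol's exact interval at 1 h is gone, and SAP 5.3.2 puts no interval in its place. SAP 6.2 does not mention that loss.

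**Working it through.** **1. The plan's own figure.** Protocol 14.2 states: "With a sample size of 15, the probability to observe at least one case of precipitated withdrawal is 79.4" per cent at a true rate of 10%, and 53.7% at 5%. Check: 1 − 0.90^15 = 0.794 and 1 − 0.95^15 = 0.537. Both reproduce. So does the rest of Protocol Table 4 (SAP Table 5), apart from the last digit of one cell (0.8329 against 0.832). The sample size is thus argued from a binomial count out of 15, the quantity the protocol analysis reports.

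**2. The rules side by side, for a subject who misses one key timepoint but has later COWS data.**

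| Subject | Protocol 14.4.1, at 48 h | SAP Table 7 |
|---|---|---|
| No event by 48 h | In the denominator, no event | Censored at the key timepoint before the gap |
| Event after the gap | Event | Event, timed at the next key timepoint |

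Censoring therefore depends on outcome. A subject who misses only the 1 h COWS and has no event is censored at time 0, although SAP Table 4 schedules 12 further assessments up to 48 h.

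**3. Direction at 48 h.** Table 7 keeps every event within 48 h and censors only event-free subjects. In the product-limit estimate each event carries a weight of at least 1/n, and more than 1/n only if someone was censored at an earlier key timepoint. So on the same n subjects the 48 h Kaplan-Meier estimate is at least d/n, where d is the number of events. The two are equal unless an event follows a censoring.

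**4. Size, under assumed data.** The documents give no outcomes and no missingness rate. Assume 15 subjects in the SAP-defined FAS, one event by 1 h, one event between 12 and 24 h, and gaps only in event-free subjects. The protocol percentage at 48 h is 2/15 = 13.3% in every row.

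| Event-free subjects with a gap | Kaplan-Meier at 48 h |
|---|---|
| None | 1 − (14/15)(13/14) = 13.3% |
| 5 miss only 12 h | 1 − (14/15)(8/9) = 17.0% |
| 5 miss only 1 h | 1 − (9/10)(8/9) = 20.0% |
| 8 miss only 12 h | 1 − (14/15)(5/6) = 22.2% |
| 10 miss only 12 h | 1 − (14/15)(3/4) = 30.0% |

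A second example shows the asymmetry directly. Take three events: at 1 h, at 6 h, and at 24 h in a subject who missed 6 h. Four event-free subjects also miss 6 h. The protocol gives 3/15 = 20.0%. Kaplan-Meier gives 1 − (14/15)(9/10)(8/9) = 25.3%. Five subjects share the same gap; four are censored at 1 h and one counts as an event at 24 h.

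With no events, both methods give 0% whatever the gaps.

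**5. The interval.** For 0/15 the Clopper-Pearson upper limit is 1 − 0.025^(1/15) = 21.8%. For 2/15 the limits are 1.7% and 40.5%.

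**The case against.** The case for leaving the SAP alone has substance. The change is disclosed twice (SAP 1.1 and 6.2), Kaplan-Meier was already named in v1.0, and Protocol 14.1 allows departures to be set out in the SAP. The adjudication analysis, added because missingness might be informative, gives a count with an exact interval, cumulative by timepoint if there are events. Derived endpoints are listed for the FAS (SAP 5.3), individual COWS plots are planned (SAP 5.3.9), and COWS values are listed chronologically (SAP 5.5.2). Table specifications are in a separate document that is not available here. In the first example the gap of 3.7 percentage points is small beside an interval of 1.7% to 40.5%.

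Most of this stands and limits the point. It does not remove it: adjudicated events follow a different definition, and a listing from which a count could be rebuilt is not a planned estimate with an interval.

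A reader might go further and infer three things that the documents do not support:

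- *That the method was chosen with outcomes in view, or to flatter the result.* The open-label design makes knowledge of outcomes possible, but the SAP cites only missing assessments and nowhere says events had been tabulated. The 48 h direction is also unfavourable to the product, if it moves at all.
- *That nobody could tell whether the answer moved.* The listings and plots would allow a reconstruction.
- *That the methods diverge whenever missingness is heavy.* They diverge at 48 h only if an event follows a censoring.

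One further caution is fair. The protocol's FAS asks for COWS assessments for 48 hours after injection. Read strictly, that could exclude the five subjects with gaps and give 2/10 = 20.0%, above the Kaplan-Meier 17.0%. A restored analysis must therefore say which FAS it uses.

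**Conclusion.** The point holds as a reporting gap that should be closed. The prespecified analysis was replaced after the extent of missing COWS was known, and the SAP does not retain it. The replacement censors by a rule that depends on outcome, so on the same subjects its 48 h estimate is equal to or above the crude percentage.

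The sizes are illustrative: 17.0% to 30.0% against 13.3%, given 15 subjects, two events at the assumed times, and 5 to 10 event-free subjects each missing one key timepoint. The true gap could be zero. The loss of the stated 1 h interval does not depend on these assumptions, although the separate table specifications might supply one. Nothing here shows favourable bias, and Kaplan-Meier can remain the main analysis.

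**What to change.** Add to SAP 5.3.3:

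> As a sensitivity analysis beside the Kaplan-Meier estimate, the number and percentage of subjects whose COWS total score has risen by 6 or more by 1, 6, 12, 24 and 48 h will be reported in the FAS of SAP Table 6, using the numerator and denominator rules of Protocol 14.4.1. Each percentage will have a two-sided 95% Clopper-Pearson interval (prespecified for 1 h, extended here to the other timepoints).

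The protocol writes its denominator rule only for 6 h onwards. The SAP should say that the same rule applies at 1 h, so that a subject in the wider FAS with no COWS by then is not counted as event-free.

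In SAP 6.2, state that the protocol's count-and-percentage analysis and its exact interval became a sensitivity analysis after the extent of missing COWS was known. The text should make no claim either way about outcome review unless the sponsor can document it.

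Cost: one extra descriptive table from data already being derived, and a few lines of SAP text. No new data collection is needed.

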6.3 Appendix 3: Definition and Use of Visit Windows in Reporting

Nominal visits will be used for the analysis without regard to visit windows.

The mapping of the protocol/CRF visits to the analysis visits will be implemented as follows in Table 11. Unscheduled visits will be given an analysis visit number in sequential order according to chronological date/time following the most recent scheduled visit.

Table 11 Visit Mappings for Analysis

Protocol/CRF Visit number (VISITNUM)	Protocol/CRF VISIT (VISIT)	Planned time point number/hour (--TPTNUM)	Planned timepoint name /Hour (-TPT)	Analysis Visit Number (AVISITN)	Analysis Visit (AVISIT)	Analysis Timepoint Number (ATPT)	Analysis Timepoint (ATPT)
1	Screening (-30 to -1)	.		1	Screening		
	Unscheduled ¹			1.1	Day 1 (Check-in) ¹		
	Unscheduled ¹			1.2	Pre-First TM BUP ¹		
	Unscheduled ¹			1.3	Post-First TM BUP ¹		
2	Day 1 (Check-in)	.		2	Day 1 (Check-in)		
3	Pre-TM BUP	.		3	Pre-TM BUP		
5	Pre-Sublocade	.		5	Pre-Sublocade		
7	Post-Sublocade	1	1 Hour Post Sublocade Dose	7	Post-Sublocade	1	1 Hour

Protocol/CRF Visit number (VISITNUM)	Protocol/CRF VISIT (VISIT)	Planned time point number/hour (-TPTNUM)	Planned timepoint name /Hour (-TPT)	Analysis Visit Number (AVISITN)	Analysis Visit (AVISIT)	Analysis Timepoint Number (ATPT)	Analysis Timepoint (ATPT)
7	Post-Sublocade	2	2 Hours Post Sublocade Dose	7	Post- Sublocade	2	2 Hours
7	Post-Sublocade	3	3 Hours Post Sublocade Dose	7	Post- Sublocade	3	3 Hours
7	Post-Sublocade	4	4 Hours Post Sublocade Dose	7	Post- Sublocade	4	4 Hours
7	Post-Sublocade	6	6 Hours Post Sublocade Dose	7	Post- Sublocade	6	6 Hours
7	Post-Sublocade	8	8 Hours Post Sublocade Dose	7	Post- Sublocade	8	8 Hours
7	Post-Sublocade	12	12 Hours Post Sublocade Dose	7	Post- Sublocade	12	12 Hours
7	Post-Sublocade	16	16 Hours Post Sublocade Dose	7	Post- Sublocade	16	16 Hours
7	Post-Sublocade	20	20 Hours Post Sublocade Dose	7	Post- Sublocade	20	20 Hours
8	Day 2	24	24 Hours Post Sublocade Dose	8	Day 2	24	24 Hours
8	Day 2	30	30 Hours Post Sublocade Dose	8	Day 2	30	30 Hours

Protocol/CRF Visit number (VISITNUM)	Protocol/CRF VISIT (VISIT)	Planned time point number/hour (-TPTNUM)	Planned timepoint name /Hour (-TPT)	Analysis Visit Number (AVISITN)	Analysis Visit (AVISIT)	Analysis Timepoint Number (ATPT)	Analysis Timepoint (ATPT)
8	Day 2	36	36 Hours Post Sublocade Dose	8	Day 2	36	36 Hours
9	Day 3	48	48 Hours Post Sublocade Dose	9	Day 3	48	48 Hours
10	Day 8	.		10	Day 8		
11	Day 15	.		11	Day 15		
12	Day 22	.		12	Day 22		
13	EOT	.		13	EOT		
14	EOS			14	EOS		

¹If there are multiple induction doses of TM BUP, the corresponding visits will be slotted in sequential order between the Screening Visit (Analysis Visit 1) and the Day 1 (Check-in) Visit (Analysis Visit 2) for the last induction dose of TM BUP.

6.4 Appendix 4: Definition of Protocol Deviations

A protocol deviation is any change, divergence, or departure from the study design or procedures defined in the protocol. Important protocol deviations are a subset of protocol deviations that may significantly impact the completeness, accuracy and/or reliability of the study data or that may significantly impact a subject's rights, safety, or wellbeing.

The important deviations will not be considered in the statistical analyses or in the definitions of analysis populations. All deviations will be listed.

